#### **INFORMED CONSENT PROCEDURES:**

Before protocol-specified procedures are carried out, consenting professionals will explain full details of the protocol and study procedures as well as the risks involved to participants prior to their inclusion in the study. Participants will also be informed that they are free to withdraw from the study at any time. All participants must sign an IRB/PB-approved consent form indicating their consent to participate. This consent form meets the requirements of the Code of Federal Regulations and the Institutional Review Board/Privacy Board of this Center. The consent form will include the following:

1. The nature and objectives, potential risks and benefits of the intended study.
2. The length of study and the likely follow-up required.
3. Alternatives to the proposed study. (This will include available standard and investigational therapies. In addition, patients will be offered an option of supportive care for therapeutic studies.)
4. The name of the investigator(s) responsible for the protocol.
5. The right of the participant to accept or refuse study interventions/interactions and to withdraw from participation at any time.

Before any protocol-specific procedures can be carried out, the consenting professional will fully explain the aspects of patient privacy concerning research specific information. In addition to signing the IRB Informed Consent, all patients must agree to the Research Authorization component of the informed consent form.

Each participant and consenting professional will sign the consent form. The participant must receive a copy of the signed informed consent form.

### **PROTECTION OF HUMAN SUBJECTS:**

#### **PRIVACY**

MSKCC's Privacy Office may allow the use and disclosure of protected health information pursuant to a completed and signed Research Authorization form. The use and disclosure of protected health information will be limited to the individuals described in the Research Authorization form. A Research Authorization form must be completed by the Principal Investigator and approved by the IRB and Privacy Board.

#### **SERIOUS ADVERSE EVENT (SAE) REPORTING**

Any SAE must be reported to the IRB/PB as soon as possible but no later than 5 calendar days. The IRB/PB requires a Clinical Research Database (CRDB) SAE report be submitted electronically to the SAE Office at [PPD](#). The report should contain the following information:

Fields populated from CRDB:

- Subject's name (generate the report with only initials if it will be sent outside of MSKCC)
- Medical record number
- Disease/histology (if applicable)
- Protocol number and title

Data needing to be entered:

- The date the adverse event occurred
- The adverse event
- Relationship of the adverse event to the treatment (drug, device, or intervention)
- If the AE was expected
- The severity of the AE
- The intervention
- Detailed text that includes the following
  - A explanation of how the AE was handled
  - A description of the subject's condition
  - Indication if the subject remains on the study
  - If an amendment will need to be made to the protocol and/or consent form.

The PI's signature and the date it was signed are required on the completed report.  
For IND/IDE protocols:

The CRDB AE report should be completed as above and the FDA assigned IND/IDE number written at the top of the report. If appropriate, the report will be forwarded to the FDA by the SAE staff through the IND Office.

### **DEFINITION OF SAE**

**An SAE** is an undesirable experience that meets one of the following criteria:

- Is fatal or life-threatening
- Is disabling
- Results in hospitalization or prolongation of hospitalization
- Results in a congenital anomaly or occurrence of malignancy
- Important medical event that jeopardizes the participant AND requires medical or surgical intervention to prevent one of the outcomes above *Note: Hospital admission for a planned procedure/disease treatment is not considered an SAE.*

### **Attribution:**

- Unrelated: The AE is *clearly NOT related* to the intervention
- Unlikely: The AE is *doubtfully related* to the intervention
- Possible: The AE *may be related* to the intervention
- Probable: The AE is *likely related* to the intervention
- Definite: The AE is *clearly related* to the intervention

### **Expected and Unexpected Event:**

- Expected: Any experience *previously reported* (in nature, severity, or incidence) in the current Investigator's Brochure or general investigational plan
- Unexpected: Any experience *not previously reported* (in nature, severity, or incidence) in the current Investigator's Brochure or general investigational plan

### **UNEXPECTED EVENT:**

- Grades 1-2: Adverse Event Reporting NOT required.
- Grades 3: Possible, Probable or Definite attribution to the drug and/or device will be reported\*.
- Grades 4 and 5: Regardless of Attribution will be reported\*.

### **EXPECTED EVENT**

- Grades 1 – 3: Adverse Event Reporting NOT required.
- Grades 4 and 5: Regardless of Attribution will be reported\*.

\*Reportable events are those which occur within 30 days of the last dose of treatment on protocol. Events beyond 30 days will be reported at the discretion of the PI.

CTCAE	Common Toxicity Criteria for Adverse Events
DLT	dose-limiting toxicity
DNA	deoxyribonucleic acid
DOR	duration of response
DRR	durable response rate
EBV	Epstein-Barr virus
EBV-CTLs	EBV cytotoxic T lymphocytes
EBV-PTLD	EBV post-transplant lymphoproliferative disorder
EBV-LPD	EBV-associated lymphoproliferative disease
LMS	leiomyosarcoma
LLOQ	lower limit of quantification
GvHD	graft-versus-host disease
HCT	hematopoietic (stem) cell transplant
HLA	human leukocyte antigen
IPD	important protocol deviations
NE	not evaluable
NPC	nasopharyngeal carcinoma
ORR	objective response rate
OS	overall survival
PD	progressive disease
PFS	progression-free survival
PID	primary immunodeficiency
PR	partial response
PTLD	post-transplant lymphoproliferative disorder
R/R	refractory/relapsed
SAE	serious adverse event
SAP	statistical analysis plan

Abbreviation	Definition
SD	stable disease [used in context of response assessment] standard deviation [used in context of analysis methods]
SOC	system organ class
SOT	solid organ transplant
SOP	standard operating procedure
tab-cel	tabelecleucel
TESAE	treatment-emergent serious adverse event
TPP	time to progression
TTR	time to response
ULOQ	upper limit of quantification

1 INTRODUCTION

The purpose of this statistical analysis plan (SAP) is to provide details of the statistical analyses that have been outlined within version A23 of the tabelecleucel (ATA129; tab-cel®) Study 95-024 protocol, dated 14 March 2018.

2 STUDY OVERVIEW

2.1 Study Objectives

- To evaluate in a phase 1/2 dose-escalating trial both the toxicities and therapeutic potential of adoptive immunotherapy with Epstein-Barr virus (EBV)-specific cytotoxic T lymphocytes (EBV-CTLs) derived from human leukocyte antigen (HLA)-histocompatible or at least HLA-haplotype-matched related donors in the treatment of EBV-induced lymphomas or other EBV-associated malignancies in severely immunocompromised hosts and organ allograft recipients who are at high risk for this complication, and to complete a single selected dose level phase 2 extension of this study to identify the probability of achieving a complete response (CR) of EBV lymphoma with EBV-specific T-cell therapy in allogenic hematopoietic stem cell transplant (HCT) recipients and immunodeficient patients.
- To evaluate the in vivo biodistribution, expansion and duration of engraftment of successive doses of transferred EBV-reactive lymphocytes within immunocompromised histocompatible or HLA-haplotype matched hosts afflicted with EBV-associated lymphoproliferative diseases and to correlate these findings with the diseased hosts' T-cell populations, general immune status and capacity to generate allospecific antidonor response.
- To determine the incidence, kinetics and durability of pathological and/or clinical responses of EBV-induced lymphomas to treatment with infusions of EBV-CTLs derived from histocompatible EBV-seropositive related donors.

2.3 Sample Size

The initial rationale for the sample size of this study was the following: For subjects in group 1, the phase 2 portion of the study was to accrue a minimum of 20 subjects and a maximum of 47 subjects, using a Simon two-stage design. Enrollment of 20 subjects is needed in the first stage. If 8 or more subjects achieve CR then we 27 additional subjects will be enrolled, for a total of 47 subjects. If at least 20 subjects achieve CR then this regimen will be recommended for further evaluation. This design has 90% power to distinguish between CR of 35% and 55% with a type I error of 10%.

2.4 Source of Study Treatment

As specified in Section 2.2, study treatment administered to subjects in this study included the following 3 types of EBV-CTL products.

2.4.1 *Third-party Cytotoxic T Lymphocytes*

Tabelecleucel, or third-party EBV-CTLs, refer to EBV-targeted CTLs generated from high resolution HLA-typed, EBV-seropositive, unrelated third-party donor T cells: ie, CTLs generated from a donor other than the subject's original allogeneic SOT or HCT transplant donor.

In this study, subjects could change to tabelecleucel with a different HLA restriction from a different donor either due to a lack of efficacy from the current cell line or insufficient supply.

Only the change to tabelecleucel with a different HLA restriction due to lack of efficacy is considered as treatment switch ("Restriction Switch")

2.4.2 *Transplant donor derived Cytotoxic T Lymphocytes*

Transplant donor-derived EBV-CTLs refers to T cells generated from the subject's original allogeneic SOT or HCT donor.

2.4.3 *Autologous Cytotoxic T Lymphocytes*

Autologous EBV-CTLs refers to T cells generated from the subjects themselves.

3 STUDY ENDPOINTS

Response-related endpoints were not specified in the protocol and are, therefore, defined in this SAP. The efficacy analyses of these response-related endpoints will be based on the disease assessments by the investigator.

3.1 Primary Endpoint

- Objective response rate (ORR)

3.2 Secondary Endpoints

- Overall survival (OS)
- Duration of response (DOR)
- Progression-free survival (PFS)
- Durable response rate (DRR)
- Time to progression (TTP)
- Time to response (TTR)

4 ANALYSIS SETS AND SUBGROUPS

In general, summary tables will include only the subjects in the specified analysis set or subgroup, and cohorts will be presented as columns.

4.1 Full Analysis Sets

The Full analysis set is defined as all subjects who received at least 1 dose of study treatment. All efficacy and safety analyses will use the full analysis set except for the endpoints of DOR and TTR, which will be conducted on the subjects in the full analysis set with an objective response (CR or partial response [PR]).

4.2 Subject Cohorts

Analysis cohorts are defined based on subjects' disease background, prior EBV⁺ disease therapy, and source of study treatment received (as defined in Section 2.4). The cohort definitions are specified in [Table 1](#). With respect to prior EBV⁺ disease therapy, subjects with prior rituximab therapy data reported will be assigned to the relevant refractory/relapsed (R/R) rituximab cohort; subjects with no prior rituximab therapy data reported will be assigned to the rituximab-naïve cohort.

All analyses will be presented by the cohorts and combined cohorts defined in this SAP, not by the groups defined in the protocol. Cohorts to be used in the analysis depend on the data availability.

Table 1: Cohorts

Cohort Number	Cohort Name	Subjects Enrolled in The Study
1	Tab-cel HCT EBV ⁺ PTLD R/R Rituximab	Y
2	Tab-cel HCT EBV ⁺ PTLD Rituximab Naïve	Y
3	Tab-cel SOT EBV ⁺ PTLD R/R Rituximab	N
4	Tab-cel SOT EBV ⁺ PTLD R/R Rituximab + Chemo	Y
5	Tab-cel AID LPD	Y
6	Tab-cel PID LPD	Y
7	Tab-cel Lymphoma	N
31	Tab-cel LMS	Y
32	Tab-cel NPC	Y
61	Tab-cel Other Solid Tumor	N
71	Tab-cel Viremia	N
101	EBV-CTL (Transplant donor derived) HCT EBV ⁺ PTLD R/R Rituximab	Y
102	EBV-CTL (Transplant donor derived) HCT EBV ⁺ PTLD Rituximab Naïve	Y
103	EBV-CTL (Transplant donor derived) SOT EBV ⁺ PTLD	Y
106	EBV-CTL (Transplant donor derived) PID LPD	Y
107	EBV-CTL (Transplant donor derived) Lymphoma	Y
171	EBV-CTL (Transplant donor derived) Viremia	Y
201	Autologous	Y

Abbreviations: AID, acquired immunodeficiency; chemo, chemotherapy; CTL cytotoxic T lymphocyte; EBV, Epstein-Barr virus; HCT, hematopoietic cell transplant; LPD, lymphoproliferative disorder; N, no; NPC, nasopharyngeal carcinoma; PID primary immunodeficiency; post-transplant lymphoproliferative disorder; R/R, refractory/relapsed; SOT, solid organ transplant; tab-cel, tablecleucel; Y, yes

Disposition, demographics, baseline characteristics, exposure and safety will be summarized as in the following headers:

Table a: HCT Cohorts:

Tab-cel HCT EBV+ PTLD				EBV-CTL (Transplant donor derived)			Total (cohort 1, 2, 101, 102)
R/R	Rituximab	R/R	Rituximab	Naïve	Total		
Rituximab (cohort 1)	Naïve (cohort 2)	Total (cohort 1+2)	(cohort 101)	Naïve (cohort 102)	Total (cohort 101+102)		

Table b: *SOT Cohorts*:

Tab-cel SOT EBV+ PTLD R/R Rituximab+Chemo (cohort 4)	EBV-CTL (Transplant donor derived) SOT EBV+ PTLD (cohort 103)	Total (cohort 4+103)
--	---	-------------------------

Table c: *Other cohorts and All cohorts*:

Other EBV+ Disorders with ID	HCT/SOT EBV+ PTLD	EBV+ Malignancy without ID
		EBV-CTL Tab-cel
		(Transplant donor derived) NPC Total (cohort 32) (cohort 107+32)
	Total	Lymphoma
AID LPD PID LPD Viremia LMS (cohort 5, (cohort 1,2,101,102, (Cohort 107)	(cohort 6+106, (cohort 106, 101, 102, 103)	Total (all cohorts)
(cohort 5) 6+106) 171) 31) 171, 31) 4, 103) 107)		

Table d: *Other cohorts and All cohorts – tabelecleucel only*:

Other EBV+ Disorders with ID	HCT/SOT EBV+ PTLD	EBV+ Malignancy without ID
		Tab-cel Total
AID PID LMS (cohort 1,2, (cohort 101,102, (Cohort 1+2) (Cohort 4) (cohort 1,2,4) Tab-cel Total (cohort 5) LPD LPD (cohort 31) 4, 103) (Cohort 103) (Cohort 4) 32) (all cohorts)	HCT EBV+ SOT EBV+ Total NPC (cohort 32) (cohort 1,2,4) 32) tab-cel	

Efficacy will be summarized as in the following headers:

Table a: HCT Cohorts:

Tab-cel HCT EBV ⁺ PTLD				EBV-CTL (Transplant donor derived)			
R/R	Rituximab	R/R	Rituximab	EBV ⁺ PTLD	Total	(cohort	Total
Rituximab	Naïve	Total	Rituximab	Naïve	(cohort	(cohort 1)	(cohort 102)
(cohort 1)	(cohort 2)	(cohort 1+2)	(cohort 101)	(cohort 102)	101+102)		

Table b: *SOT Cohorts:*

Tab-cel SOT EBV ⁺ PTLD R/R	EBV-CTL (Transplant donor derived) SOT EBV ⁺ PTLD
Rituximab+Chemo (cohort 4)	(cohort 103)

Table c: *Other cohorts and All cohorts:*

Other EBV ⁺ Disorders with ID				EBV ⁺ Malignancy without ID		
AID	PID	Viremia	LMS	EBV-CTL (Transplant donor derived)	Lymphoma	Tab-cel NPC
LPD (cohort 5)	(cohort 6+106)	(cohort 171)	(cohort 31)	(Cohort 107)		(cohort 32)

Table d: *Other cohorts and All cohorts – tabelecleucel only:*

Other EBV ⁺ Disorders with ID				EBV ⁺ Malignancy without ID
AID (cohort 5)	PID (cohort 6)	Viremia (cohort 31)	LMS (cohort 31)	Tab-cel NPC (cohort 32)

Cohort Assignment for Subjects with > 1 Source of Study Treatment

Some subjects may receive EBV-CTLs from > 1 donor source type (Section 2.4) during the study. As a general rule for efficacy analysis, any transplant donor-derived or autologous EBV-CTL treatment received after the initiation of tabelecleucel will be considered as other anti-underlying EBV⁺ disease therapy. For such subjects, the efficacy analysis may be censored due to the initiation of this therapy in sensitivity analysis.

The efficacy and safety data for a subject who starts with tabelecleucel and then switches to either transplant donor-derived or autologous EBV-CTLs will be presented under the relevant tabelecleucel cohort.

Each subject who first receives an EBV-CTL product other than tabelecleucel and then switches to a different non-tabelecleucel EBV-CTL product (eg, transplant donor-derived followed by autologous) will be considered as 2 independent subjects for the purposes of analysis. The efficacy and safety data for such a subject will be assigned to the relevant study treatment source cohort based on the initial dose of each product type.

A subject who first receives an EBV-CTL product other than tabelecleucel, switches to tabelecleucel, and then switches to a non-tabelecleucel EBV-CTL product, will be considered as 2 independent subjects, based on the first 2 study treatments received, for the purposes of analysis. The efficacy and safety data for such a subject will be assigned to the relevant study treatment source cohort based on the initial dose of the first 2 product types. The third EBV-CTL product will be considered as other anti- post-transplant lymphoproliferative disorder (PTLD) therapy.

Data for subjects assigned to the autologous EBV-CTL cohort will not be included in the summary tables or figures. The efficacy and safety data for these subjects during autologous EBV-CTL treatment will be provided in the listings.

Regardless of the number of products received, all subjects will be counted only once in the ‘Overall Total’ combined cohort for safety analyses.

4.3 Subgroups

Some of the safety and efficacy analyses may be repeated for the following subgroups within the full analysis set, if plausible considering the number of subjects in the subgroups.

- Age (< 18 vs. \geq 18, $<$ 16 vs. \geq 16)
- Gender (male vs. female)
- Race (White, Other races, Unknown or Missing)

Other subgroups may be included in the analysis depending on the availability of the data.

5 INTERIM ANALYSIS AND EARLY STOPPING GUIDELINES

No formal interim analysis is planned.

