For patients in Group I, the phase II aspect of the trial will accrue a minimum of 20 patients and a maximum of 47 patients. We observed a complete remission rate using a Simon two-stage design. We will enroll 20 patients in the first stage. If 8 or more achieves CR then we will enroll 27 more for a total of 47 patients. If there are at least 20 patients achieving CR then we will recommend this regimen for further evaluation. This design has 90 % power to distinguish between CR rates of 35 % and 55 % with a Type I error of 10 %.

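### SAP Section 5 says there is no interim analysis, yet the two-stage design in SAP 2.3 has a stop/continue look after 20 patients; the quoted 10% error and 90% power do not fit the written rule with or without that look

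*SAP*

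**What the plan says.** The protocol (Biostatistics, Group I phase II) sets a first stage of 20 patients and then a condition: "If 8 or more achieves CR then we will enroll 27 more for a total of 47 patients". The regimen is recommended for further evaluation if at least 20 CRs are seen. The stated operating characteristics are 90% power and 10% type I error for CR rates of 35% and 55%.

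SAP 2.3 repeats the design. It opens with "The initial rationale for the sample size of this study was the following", then gives the first stage ("Enrollment of 20 subjects is needed in the first stage"), the gate ("If 8 or more subjects achieve CR then we 27 additional subjects will be enrolled, for a total of 47 subjects"), the final rule ("If at least 20 subjects achieve CR then this regimen will be recommended for further evaluation") and the same error rates.

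SAP Section 5, whose title covers both interim analysis and early stopping, consists of one sentence: "No formal interim analysis is planned".

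SAP Section 11 lists three changes from the protocol: no formal test on CR, objective response rate (ORR) in place of CR as primary endpoint, and presentation by SAP cohorts in place of protocol groups. The stage-1 look is not on the list.

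**The concern.** A rule that lets patient 21 enter only if 8 of the first 20 responded is an interim futility decision on accumulating response data. Sections 2.3 and 5 of the same SAP therefore conflict unless something explains how they fit together, and nothing does. The SAP can be explicit about abandoned design elements: Section 2.2 says that the dose-escalation scheme was not followed and that dose-limiting toxicity data were not collected. For the stage-1 look a reader cannot tell whether it was assessed, met, missed or dropped.

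This matters because the error rate of a two-stage rule depends on whether the first stage operated. If fewer than 8 of the first 20 responded and enrolment went on, the protocol's own rule would not have allowed the further patients, yet a later total of 20 or more CRs would still look like a success. A reader who relies on the rates in 2.3 would also take the design to be stricter than the written rule is, whichever way accrual went.

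**Working it through.** **Inputs** (protocol Biostatistics; SAP 2.3): null CR rate 0.35, target CR rate 0.55; stage 1 of 20 patients, continue at 8 or more CRs; 27 more, total 47; recommend at 20 or more CRs. Stated: type I error 10%, power 90%. The documents do not state sidedness; I take the error as one-sided, as is inherent in a single-arm rule of this kind.

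**Formulas** (exact binomial; c is the final cut-off, p the true CR rate, X1 the CRs in stage 1, X2 the CRs among the next 27)

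- Look applied: P(recommend) = Σ over x = 8 to 20 of P(X1 = x | 20, p) × P(X2 ≥ c − x | 27, p)
- Look not applied: P(recommend) = P(X ≥ c | 47, p)
- Early stop: P(X1 ≤ 7 | 20, p)

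**Step 1. Try to reproduce the stated 10% and 90%.** With the look and c = 20, as written, the result is 14.17% at p = 0.35 and 92.46% at p = 0.55. The stated figures do not reproduce.

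**Step 2. Vary the look and the cut-off.**

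| Rule | Type I error (35%) | Power (55%) |
|---|---|---|
| Look applied, at least 20 of 47 (as written) | 14.17% | 92.46% |
| Look not applied, at least 20 of 47 | 17.49% | 96.84% |
| Look applied, at least 21 of 47 | 9.38% | 90.49% |
| Look not applied, at least 21 of 47 | 10.89% | 94.13% |

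Only the third row meets both stated rates. A search over Simon designs for 35% against 55% at 10% error and 90% power returns that row as the optimal design: stop at 7 or fewer of 20, and declare failure at 20 or fewer of 47. The expected sample size under the null is 20 + 27 × (1 − 0.601) = 30.8. The quoted rates thus fit a rule of more than 20 CRs with the look in force, whereas both documents say at least 20.

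**Step 3. Split the excess over 10% when the look is not applied.**

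- Total: 17.5 − 10.0 = 7.5 points
- Final cut-off, with the look kept: 14.2 − 10.0 = 4.2 points
- Loss of the look: 17.5 − 14.2 = 3.3 points

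The last item is the probability, at a 35% CR rate, of fewer than 8 CRs in stage 1 followed by 20 or more in total. As a share of all trials reaching 20 or more it is 3.32 / 17.49 = 19%. At a cut-off of 21 the look is worth 10.9 − 9.4 = 1.5 points, which is enough to decide whether 10% is met.

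**Step 4. Early stopping.** P(X1 ≤ 7 | 20) is 60.1% at a CR rate of 35% and 5.8% at 55%. At 35%, then, the look spares up to 27 further patients in about 60% of trials.

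**The case against.** The strongest reply is that the SAP has already stepped away from this design. Section 2.3 calls it the initial rationale. Section 11 says that CR will not be formally tested although the sample size came from a two-stage calculation, makes ORR primary, and reports by cohort. The planned efficacy tables split Group 1 by product, rituximab history and disease, so none of them is a Group 1 CR count out of 47. The SAP also reads as largely retrospective (data transferred from the site, cohorts marked by whether subjects were enrolled). In that setting the sentence in Section 5 may mean only that the SAP adds no look of its own.

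Much of this stands, and it rules out two stronger readings.

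- A reader might infer that the look was skipped and its early-stop protection lost. The documents do not show this: the gate is still in the protocol, and a sentence in the SAP does not remove it.
- A reader might infer that the trial's analysis runs at 17.5% type I error, or that restoring the look would secure 10%. Neither holds. No SAP analysis tests CR, so the 17.5% attaches only to the protocol's 20-of-47 recommendation rule and only if the look was not applied. With the look fully honoured, the written rule is still at 14.2%.

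The reply does not remove the contradiction between 2.3 and 5, or the absence of the look from Section 11. Nor does it rescue the error rates, which 2.3 states in the present tense as properties of the design: "This design has 90% power to distinguish between CR of 35% and 55% with a type I error of 10" (per cent).

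**Conclusion.** The point holds as a contradiction within the SAP together with a misquoted error rate. Section 5 denies an interim analysis that 2.3 and the protocol describe, Section 11 is silent on it, and the 10% and 90% are wrong for the written rule in both cases: 14.2% and 92.5% with the look, 17.5% and 96.8% without it. The final cut-off contributes more of the excess error (4.2 points) than losing the look would (3.3 points).

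The calculation assumes independent responses with a common CR rate, all 47 patients counted, and the cut-offs as written. Whether the 17.5% and the loss of the 60% early-stop probability apply depends on a fact that the documents do not give, namely whether the look was made before patient 21 was enrolled. The consequence falls on the interpretation of the protocol's recommendation rule and not on the SAP's planned estimates. The correction should be made: it is cheap and puts right a stated operating characteristic.

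**What to change.** 1. **SAP Section 5.** State that the protocol's stage-1 look was the one interim decision rule. Report the number of CRs among the first 20 treated Group 1 phase II patients, in order of first dose, against the rule of 8 or more. Counting treated patients agrees with SAP 6.1, which defines enrolled subjects as those who received study treatment, and avoids bringing in an evaluable population that neither document defines for this design.
2. **SAP Section 11.** State whether the look was done before further enrolment and with what result, or that it was abandoned.
3. **SAP 2.3.** Replace the 10% and 90% whatever the answer to item 2. For at least 20 of 47, quote 14.2% and 92.5% if the look was applied, or 17.5% and 96.8% if it was not. Alternatively, reconcile the cut-off with the quoted rates: at least 21 of 47 gives 9.4% and 90.5% with the look, and 10.9% and 94.1% without it. Meeting the gate is not a reason to leave 10% and 90% beside a cut-off of 20.

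The cost is some SAP wording and one count from dose dates and responses already held. The downside is a less favourable stated error rate and, possibly, having to report that the look was not made.
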